
Study Objectives: The objectives of this study are to:
 
 - Investigate the efficacy of SelK2 as monotherapy in the prevention of VTE (composite of asymptomatic DVT detected by mandatory unilateral venography of the operated leg or confirmed symptomatic DVT, confirmed symptomatic PE or unexplained death) in patients undergoing primary unilateral TKA; - Assess the incidence of bleeding events (major bleeding events, clinically relevant non-major bleeding events, and minor bleeding events) in patients administered SelK2 and undergoing primary unilateral TKA; - Assess the overall safety and tolerability of SelK2 in this patient population; - Further describe the PK and PD of SelK2; - Evaluate the immunogenicity of single dose SelK2; and - To evaluate exploratory efficacy endpoints of inflammation and thrombosis. - Adaptive arm, if activated, assess the efficacy and safety of SelK2 when given in addition to enoxaparin for the prevention of venous thromboembolism (VTE) in patients undergoing primary unilateral TKA. 	

Study Design: This clinical study is a multi-center, randomized, active comparator-controlled, open-label, adaptive design study to assess the safety and efficacy of SelK2 in the prevention of VTE events in patients undergoing TKA. A total of approximately 190 patients planning to undergo unilateral TKA will be recruited into two arms of the study.
 
The two arms of the study will enroll patients in a 1:1 ratio (approximately 95 patients in each arm) as shown below:
 
 1.) 7.5 mg/kg SelK2 (IV, single-dose) 2.) Active Comparator (40 mg Enoxaparin, SC, QD) 
Patients planning to undergo scheduled TKA under general anesthesia who meet all the inclusion criteria and none of the exclusion criteria will be eligible for randomization into this study. Prior to randomization, a Screening Phase consisting of clinical and laboratory evaluations will occur within 30 days prior to randomization to assess patient eligibility for this study. Upon meeting all criteria, patients will be randomized into this study using a centralized randomization system.
	

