Following randomization, patients randomized to the SelK2 arm will receive a single dose of 7.5 mg/kg SelK2 via intravenous (IV) administration over a 30-minute time period at least 12 hours but not longer than 24 hours prior to the start of the TKA procedure. Patients randomized to the enoxaparin arm will receive 40 mg enoxaparin administered SC 12 hours after TKA surgery followed by daily injections of 40 mg enoxaparin for at least 9 consecutive days post-surgery and up to the time point of the venography (with the option of giving an additional 40 mg enoxaparin, SC dose 12 hours prior to TKA surgery).

For all patients, the TKA procedure will be done on Study Day 2. Patients will be required to spend at least 2 nights after TKA procedure in the hospital, and patients, at the discretion of the PI, can remain in the hospital at least up to the day of the venography.

All patients will be required to undergo unilateral ascending venography of the operated leg 10 ± 2 days post-surgery (Study Day 11 ± 2 days). After completion of the venogram, patients will be released from the clinical setting, and this will conclude the Treatment Phase of the study.

The Follow-up Phase of this study will consist of two clinic visits on Days 21 and 57 and two follow-up telephone contacts on Days 29 and 43. The final study visit occurs on Day 57 (Day 57/Early Discontinuation Visit).

Data on all asymptomatic deep vein thrombosis (DVT) as determined by venogram and symptomatic clinical VTE will be collected during both Treatment and Follow-up Phases of the study. Bleeding events and other safety and clinical laboratory assessments including exploratory markers of inflammation and thrombosis, coagulation parameters and bleeding events will be performed throughout both the Treatment and Follow-up Phases. Data on all suspected arterial thrombotic events will also be collected. Blood samples will be collected for PK, PD, and immunogenicity analyses.

A Central Independent Adjudication Committee (CIAC) will assess all venograms, symptomatic VTE outcomes (including DVT and PE), bleeding events, suspected stroke, any other suspected arterial thrombotic events, and death. Adjudicators will be blinded to treatment assignment.

A Steering and Safety Committee will conduct ongoing reviews of all safety and efficacy data in an unblinded fashion.

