[REDACTED] Vials are stored refrigerated at 2 to 8°C and protected from light. A pharmacist or designated personnel will compound individual doses of active study drug for patients on a milligram per kilogram basis in a 100 mL infusion bottle or bag of a sterile 0.9% sodium chloride solution (0.9% Sodium Chloride Injection, USP) in accordance with the Pharmacy Manual. Study drug will be administered over 30 minutes by IV infusion.

Active Comparator (Enoxaparin): Commercially available enoxaparin (40 mg in 0.4 mL water

in pre-filled disposable syringes for SC administration) will be provided to the study site pharmacies for use in this study, in accordance with local regulatory requirements. Enoxaparin should be stored in a temperature-controlled environment which is maintained below 25°C; but should not be frozen.

The Pharmacy Manual will provide further details about handling, storage, and mode of administration.

Dose Rationale:

Criteria for Evaluation:

Primary Efficacy Endpoints: The primary efficacy outcome is the composite of asymptomatic deep vein thrombosis (DVT) detected by mandatory unilateral venography of the operated leg or confirmed symptomatic DVT, confirmed symptomatic PE or unexplained death during the Treatment Phase. All efficacy endpoint data will be adjudicated by a blinded Central Independent Adjudication Committee.

Exploratory Efficacy Endpoints: The exploratory efficacy outcomes will include measurements of markers of inflammation and thrombosis (hsCRP and D-dimer, respectively) and other possible PD markers of SelK2 efficacy.

PK, PD, and Immunogenicity Evaluations: Samples will be collected during Treatment and Follow-up Phases for evaluation of PK, PD, and immunogenicity.

Safety:

The primary safety outcome is a composite of major bleeding events or clinically relevant non-major bleeding events during the Treatment Phase. The secondary safety outcomes are the incidence of the composite of major, clinically relevant non-major, or minor bleeding events that occur during the Treatment and Follow-up Phases.

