1.5 Rationale for the Dose Regimen

2.0 STUDY OBJECTIVES

The objectives of this study are:

Primary:

- To investigate the efficacy of SelK2 as monotherapy for the prevention of VTE (composite of asymptomatic DVT detected by mandatory unilateral venography of the operated leg or confirmed symptomatic DVT, confirmed symptomatic PE or unexplained death) in patients undergoing primary unilateral TKA.
- To assess the incidence of bleeding events (major bleeding events, clinically relevant non-major bleeding events, and minor bleeding events) in patients administered SelK2 and undergoing primary unilateral TKA.
- To assess the overall safety and tolerability of SelK2 in this patient population.

Secondary:

- To further describe the PK and PD of SelK2.
- To evaluate the immunogenicity of single dose SelK2.
- To evaluate exploratory efficacy endpoints of inflammation and thrombosis.

Adaptive Arm (SelK2 given concomitantly with enoxaparin; SelK2, 7.5 mg/kg, IV and enoxaparin, 40 mg, SC, QD):

- Assess the efficacy and safety of SelK2 when given in addition to enoxaparin for the prevention of VTE in patients undergoing primary unilateral TKA.

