3.6 Endpoints

3.6.1 Primary Efficacy Endpoint

3.6.1.1 Incidence of Total Venous Thromboembolism

The incidence of total venous thromboembolism will consist of a composite of:

- Asymptomatic deep-vein thrombosis of the operated leg (detected by mandatory unilateral venography);
- confirmed symptomatic DVT of the leg(s);
- confirmed symptomatic pulmonary embolism; and
- unexplained death for which pulmonary embolism could not be ruled out.

A unilateral ascending venogram is to be performed on each study patient between Study Day 9 and Study Day 13 of study conduct (approximately 10 days after completion of TKA). The venogram will be obtained from the leg that underwent surgery. Multiple views of each venous segment will be obtained per instructions provided in the Manual for Venography and Event Reporting. The CIAC will review all venographic data in a blinded fashion for the adjudication of an endpoint event.

Study patients will be evaluated for signs and symptoms of DVT (e.g., swelling, localized pain, redness, heat, localized warmth) and PE (e.g., unexplained shortness of breath, coughing up blood, chest pain that gets worse with a deep breath, unexplained coughing) during the post-surgery in hospital/clinic period and at all visits occurring throughout the Treatment and Follow-up Phases of the study.

Every suspected episode of DVT or PE must be reported appropriately as an AE. The underlying clinical data from any patient with a suspected DVT or PE events will be presented to the CIAC and adjudication as a possible study endpoint.

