- Institute standard of care for life-threatening bleeding (large bore IV or central venous line, type and crossmatch blood, admit to the intensive care unit, provide hemodynamic and respiratory support);
- Administer antidotes if applicable (e.g., administer protamine if the patient had recently received heparin); and
- Administer packed red blood cells (or whole blood) as needed.

Use of prothrombin complex concentrates (PCCs), recombinant Factor VIIa, other factor procoagulants, or antifibrinolitics (depending upon the clinical situation and local availability) should be considered in consultation with a local available hematology expert. The SelK2 Medical Support Line ([contact]) can be contacted to discuss patient management (English language only).

6.5.2.1.2 *Stroke*

If a patient has a suspected stroke, the diagnostic work-up should be performed according to the hospital routine (it is expected that CT scans/MRI of the brain are done). Stroke will be reviewed by the CIAC to evaluate whether hemorrhagic stroke was present which will be considered as a major bleeding event.

6.5.2.1.3 *Death*

For patients who died, the adjudication committee will need to classify cause of death and will attribute death to PE if no other cause can be identified.

It is therefore crucial to provide a detailed description including the sequence of events preceding death (e.g. “patient gradually deteriorated and was found dead, or patient became suddenly short of breath and collapsed”).

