7.2 Adverse Events that are Potential Study Endpoint Events

Please note that AEs and SAEs that are listed below are being captured as events defined as endpoints for this clinical study (both efficacy and safety endpoints).

Symptomatic events that will be adjudicated include the following:

- Suspected symptomatic DVT
- Suspected symptomatic PE
- Suspected bleed
- Suspected stroke
- Death
- Suspected arterial thrombotic events (e.g., myocardial infarction, ischemic stroke, etc.)

Whenever the site becomes aware of one of these clinical events, it is crucial that the event is reported as soon as possible, preferably within 24 hours. These events must be reported following the rules as outlined for all adverse events in Section 7.1.

An appropriate event adjudication dossier will need to be submitted even if a suspected event is not confirmed by tests locally, for example if imaging did not confirm a new clinical event.

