10.2 Analysis Populations

Assignment of patients to analysis populations will be done prior to clinical data lock for the study. The following populations will be defined: Intent-to-Treat (ITT), modified Intent-to-Treat (mITT), Per-Protocol (PP), and Safety.

Intent-to-Treat (ITT): All patients who are randomized. The ITT population will be analyzed by randomized treatment group.

Modified Intent-to-Treat (mITT): All patients in the ITT population who also have a successful venogram or symptomatic VTE event which allow for assessment of the primary efficacy outcome.

Per-Protocol (PP): All mITT patients who complete the study and have no major protocol violations that will impact the efficacy assessments.

Safety: All patients who received at least 1 dose of study drug. Safety population will be analyzed by actual treatment received.

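### The per-protocol set requires completion to Day 57, so it drops every fatal endpoint event before then and every assessed patient who leaves early (minor).

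*Combined protocol and SAP*

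**What the plan says.** **Endpoint.** Section 3.6.1.1 lists four components of total VTE. The last, separate from confirmed symptomatic PE, is "unexplained death for which pulmonary embolism could not be ruled out". The Synopsis agrees: the composite ends with "confirmed symptomatic PE or unexplained death during the Treatment Phase".

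**mITT.** Section 10.2 admits "All patients in the ITT population who also have a successful venogram or symptomatic VTE event which allow for assessment of the primary efficacy outcome". Two routes are named, and death is not one of them. Section 10.3.3 makes mITT the main efficacy set.

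**PP.** Section 10.2 restricts PP to mITT patients who complete the study and have no major violation bearing on efficacy. Section 6.4.4 says that the Day 57 assessments mark each patient's completion. Section 10.3.2.1 counts completion of treatment visits as a separate disposition category, so study completion is not the same as treatment completion.

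**Use of PP.** Section 10.3.3 repeats the primary non-inferiority analysis on PP. It also compares the individual components on both mITT and PP, once through the Treatment Period and once with events to Day 57. It calls the PP analyses supportive only.

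**The concern.** The PP rule conditions on something that happens after the primary outcome is known. The outcome is settled at the venogram on Day 11 ± 2 days, or by an adjudicated event before it. Completion is judged about six weeks later.

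Two kinds of patient are therefore lost although their primary outcome has been assessed: those who die of an endpoint event before Day 57, and those who leave between assessment and Day 57 for any reason. The first loss depends directly on the outcome. The unexplained-death component, and any fatal PE before Day 57, is zero in PP by construction, so one of the planned component comparisons cannot return a non-zero result.

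In a non-inferiority comparison PP is commonly read as the check on the mITT result. A check that removes failures by rule is weaker than it looks.

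**Working it through.** **1. Tracing a fatal event through the definitions.**
- Unexplained death before venography. If it counts as a symptomatic VTE event, the patient enters mITT but cannot complete Day 57, so is not in PP. If it does not count, the patient is in neither set.
- Death after an evaluable venogram but before Day 57. The patient is in mITT and not in PP.
- Evaluable venogram, then withdrawal before Day 57. The patient is in mITT and not in PP, with or without an event.

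No exception is stated. The number of endpoint deaths before Day 57 that can be counted in PP is 0 on either reading of mITT.

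**2. Reproducing the planned size (Section 10.1).** Inputs: 25% in both arms, margin 15%, one-sided 90% CI, 80% power.

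n = [0.25×0.75 + 0.25×0.75] × (1.2816 + 0.8416)² / 0.15² = 75.13, rounded up to 76 per arm; 76 / 0.80 = 95 randomized. Both figures reproduce, and this point changes neither.

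**3. Size of the PP effect.** The documents name no CI method and give no death rate or rate of leaving, so the Wald limit and all counts below are assumptions.

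Upper limit = (p₁ − p₀) + 1.2816 × √[p₁(1−p₁)/n₁ + p₀(1−p₀)/n₀], with SelK2 = 1 and enoxaparin = 0.

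| Scenario | SelK2 | Enoxaparin | Difference | Upper limit |
|---|---|---|---|---|
| Planned rates, nobody dropped | 19/76 | 19/76 | 0.0% | 9.0% |
| 1 SelK2 event patient dropped | 18/75 | 19/76 | −1.0% | 8.0% |
| 3 SelK2 event patients dropped | 16/73 | 19/76 | −3.1% | 5.8% |
| 1 enoxaparin event patient dropped | 19/76 | 18/75 | +1.0% | 10.0% |
| 3 enoxaparin event patients dropped | 19/76 | 16/73 | +3.1% | 12.0% |
| Near the margin, nobody dropped | 24/76 | 19/76 | +6.6% | 15.9% |
| Same, 2 SelK2 event patients dropped | 22/74 | 19/76 | +4.7% | 14.1% |
| Same, 2 enoxaparin event patients dropped | 24/76 | 17/74 | +8.6% | 17.9% |
| 6 event-free enoxaparin patients dropped | 19/76 | 19/70 | −2.1% | 7.2% |
| 6 event-free SelK2 patients dropped | 19/70 | 19/76 | +2.1% | 11.5% |

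First line worked: √(2 × 0.1875/76) = 0.0702, and 1.2816 × 0.0702 = 0.0900. Newcombe limits for the first seven rows differ from these by at most 0.13 point.

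Each lost event patient moves the limit by about 1 point: down if from SelK2, up if from enoxaparin. The last two rows show that losing patients without events also moves it, which matters for the choice of repair.

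**4. The mITT wording.** The question is whether an unexplained death is a symptomatic VTE event for mITT entry.
- In favour: Section 2.0 defines VTE as a composite that includes "confirmed symptomatic DVT, confirmed symptomatic PE or unexplained death) in patients undergoing primary unilateral TKA"; Section 6.5.2.1.3 says the committee "will attribute death to PE if no other cause can be identified"; Section 7.2 lists death under "Symptomatic events that will be adjudicated include the following"; Section 10.5 refers to the components of a composite VTE event rate; and the closing qualifier in the mITT sentence points to whether the outcome can be assessed.
- Against: the Synopsis has the committee review "symptomatic VTE outcomes (including DVT and PE), bleeding events, suspected stroke, any other suspected arterial thrombotic events, and death", with death apart from VTE, and Section 3.5 also lists suspected VTE and unexplained deaths separately.

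The balance favours inclusion.

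**The case against.** **PP cannot change the result.** This stands. Section 10.3.3 makes PP supportive, fatal events are probably few (no rate is given), and the shift is about 1 point per patient.

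**A reader might infer that the PP rule tilts the trial towards SelK2.** The documents do not support this. The false-pass row (15.9% to 14.1%) needs two SelK2 event patients to be lost, and nothing in the documents makes that likely. The one withdrawal route that can be traced runs the other way: Section 6.5.1.2 stops prophylactic enoxaparin when an event needs therapeutic anticoagulation, and Section 8.1 allows withdrawal when study drug is stopped. SelK2 is a single dose before surgery, so that route exists only in arms receiving enoxaparin. In the SelK2-alone comparison it removes enoxaparin events and raises the limit. Even this route is only a possibility, because stopping a drug is not leaving the study and Section 8.1 is permissive.

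**A reader might infer that mITT excludes unexplained deaths.** Section 10.2 does not name them, but that is an unstated mapping and not an exclusion; the sections set out in the working favour counting them. Deaths are also adjudicated blind (Sections 3.5 and 11.4), under a charter that is not in the documents. This part is a clarification.

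**A narrower repair, excusing only event patients from Day 57, would itself select on the outcome.** This also stands. Patients with a clean venogram who leave early would still be dropped, which inflates PP event rates and can move the limit either way (7.2% or 11.5% against 9.0%, with six assumed leavers in one arm).

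**Conclusion.** The point holds for PP and is minor. Taken together, Sections 10.2 and 6.4.4 exclude from PP every fatal endpoint event before Day 57 and every patient with an assessed primary outcome who leaves before Day 57. Section 10.3.3 nevertheless plans primary and component analyses on that set. That much follows from the text alone.

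The size rests on assumptions: a Wald limit, 76 evaluable per arm, 25% event rates, and invented counts of lost patients. On those, one event patient is worth about 1 point of the upper limit, with the sign set by the arm that loses the patient. Only close to the 15% margin could PP and mITT disagree because of it. No net direction can be claimed, and the primary mITT conclusion is unaffected.

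**What to change.** **PP.** Delete the study-completion condition from the PP definition in Section 10.2. PP then consists of all mITT patients without a major protocol violation bearing on the efficacy assessments, whether or not they had an event. Nothing is needed in its place, because mITT membership already requires an assessable primary outcome.

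**mITT (optional).** Reword the entry condition as: a successful venogram or any adjudicated component of the primary endpoint, including "unexplained death for which pulmonary embolism could not be ruled out".

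**Cost.** One deletion and, if wanted, one clause. PP becomes slightly larger and closer to mITT, so it differs less as a sensitivity analysis. In the Day 57 analyses PP would hold some patients with incomplete follow-up, as mITT already does. No new data are needed, since deaths and VTE events are already adjudicated, and the planned 76 evaluable and 95 randomized per arm do not change.

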3.4.2 Treatment Phase

After assessment that the patient has met all Inclusion Criteria and none of the Exclusion Criteria, on the day PRIOR to the scheduled TKA surgery, the patient will be randomized into this study. Prior to dosing of any study drug, baseline safety assessments will be taken.

For those randomized to receive SelK2, patients will receive a single dose of 7.5 mg/kg SelK2 via IV administration at least 12 hours prior to but not longer than 24 hours prior to the start of the TKA surgery. The Treatment Phase of the study consists of the period from the dosing of study drug (SelK2 or enoxaparin) or the TKA (for enoxaparin arm, if enoxaparin dosing is only done after TKA) up to the day of venography (Day 11 \pm 2) or early study termination. Note that for patients randomized to receive SelK2, study drug can be dosed either the day prior to TKA (Day 1) or on the day of TKA (Day 2) as long as the dosing occurs at least 12 hours prior to but not longer than 24 hours prior to the start of the TKA surgery.

For those randomized to receive enoxaparin, patients will receive 40 mg enoxaparin administered via SC injection 12 hours after TKA surgery followed by daily SC injections of 40 mg enoxaparin for at least 9 additional days post-surgery (with the option of giving an additional 40 mg enoxaparin SC dose 12 hours prior to TKA surgery).

For those randomized to receive SelK2 and enoxaparin, patients will receive a single dose of 7.5 mg/kg SelK2 via IV administration at least 12 hours prior to but not longer than 24 hours prior to

the start of the TKA surgery and will receive 40 mg enoxaparin administered via SC injection 12 hours after TKA surgery followed by daily SC injections of 40 mg enoxaparin for at least 9 additional days post-surgery.

For all patients, the Treatment Phase will be completed on the day the venography is completed.

Patients will remain in the hospital for AT LEAST two overnights after TKA. During the Treatment Phase, efficacy, safety and PK/PD/Immunogenicity assessments will be completed for each patient.

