5.2 Dosage Schedule

5.2.1 Dosing of SelK2

For those randomized to receive SelK2, patients will receive a single dose of 7.5 mg/kg SelK2 via IV administration at least 12 hours prior to but not longer than 24 hours prior to the start of the TKA surgery. SelK2 will be given as an approximately 100 mL IV infusion over approximately 30 minutes (\pm 15 minutes).

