5.2.3 Adaptive Arm: Dosing of SelK2 and Enoxaparin

When the adaptive arm is activated, for those randomized to receive SelK2 and enoxaparin in combination, patients will receive a single dose of 7.5 mg/kg SelK2 via IV administration at least 12 hours prior to but not longer than 24 hours prior to the start of the TKA surgery. SelK2 will be given as an approximately 100 mL IV infusion over approximately 30 minutes (\pm 15 minutes). Additionally, patients will receive 40 mg enoxaparin administered via SC injection 12 hours after TKA surgery followed by daily SC injections of 40 mg enoxaparin through and including Day 11 (\pm 2 days).

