6.5.2.1 Adverse Events

Adverse events will be assessed by standard non-leading questions. All clinical AEs occurring from Randomization on Day 1 and up until the Day 57 visit whether observed by the investigator or reported by the patient will be assessed, documented, and reported in accordance with ICH GCP guidelines. Section 7.0 outlines the definitions, collection periods, criteria, and procedures for documenting, grading, and reporting AEs. A separate document that details AE eCRF completion guidelines for Investigators as well as training will be provided.

6.5.2.1.1 *Bleeding*

All suspected bleeding events are to be reported and additional examination will be done if deemed necessary by the investigator depending on the type of bleeding (e.g. hematology blood sample, endoscopy). If a patient has a hemorrhagic stroke both stroke and bleeding will be reviewed.

Narratives of bleeding events should be detailed and contain the following elements at the minimum:

- Location of the bleeding
- Size (in case of hematoma)
- Duration
- Provocation e.g. associated with any procedure
- Hemoglobin values prior and after bleeding if available
- Any transfusion or medication given

Other bleeding related parameters should be recorded during the trial:

- Hb level, HCT and red cell count changes during the treatment period
- Blood loss (peri-, post-operative) quantified by the routine method in each hospital
- Number of transfusions of packed red cells and transfused quantities until follow-up (e.g., 30 days after surgery; homologous and autologous transfusions need to be distinguished)

If a decrease in hemoglobin, blood loss or more transfusions are given than expected following TKA a suspect bleeding event needs to be reported and the narrative as specified above needs to be completed.

The data of all reported bleeding events or potential bleeding event must be submitted to the CIAC. The Study Site Manual for Venography and Event Reporting provides instruction for sites on the documentation, data collection, and reporting required for each suspected bleeding event.

Approach to Patients With Acute Bleeding

The following steps are recommended for patients with ongoing life-threatening bleeding (bleeding resulting in hemodynamic compromise requiring intervention or any intracranial hemorrhage):

- Withhold enoxaparin and all other anticoagulant/antiplatelets;

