10.4 Safety Analysis

All treatment-emergent AEs and SAEs will be summarized by treatment using the MedDRA coding system, by system organ class, preferred term, relationship to Study Drug and severity (See Section 10.4.1).

Incidence of bleeding events (as adjudicated by the CIAC) including the following will be tabulated by treatment:

- 1) Major Bleeding event (MB),
- 2) Clinically Relevant Non-Major Bleeding event (CRNMB),
- 3) Minor Bleeding event, or
- 4) Combination of MB and CRNMB

Additionally, the overall safety profile of study drug will be assessed in terms of the following safety and tolerability endpoints:

- Incidence of treatment-emergent adverse events (TEAEs),
- Clinical laboratory values (hematology, serum chemistries, urinalysis, and coagulation parameters),
- ECGs,
- Vital signs.

These safety endpoint measures will be tabulated by treatment arm and study visit (and timepoint, where appropriate) and may also be presented as change and percent change from baseline, as appropriate.

Safety analysis will be based on the set of data associated with the period from randomization through the final Follow-Up Phase visit (Day 57). All Safety analyses will be performed on the safety population. Descriptive analysis of the above safety parameters will be performed.

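### Bleeding is summarised only in dosed patients, by treatment actually received, so an enoxaparin patient who bleeds around surgery and is never dosed drops out of the tables

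*Combined protocol and SAP*

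**What the plan says.** Section 10.2 of the protocol defines the Safety population as "All patients who received at least 1 dose of study drug. Safety population will be analyzed by actual treatment received". Section 10.4 adds: "All Safety analyses will be performed on the safety population". No bleeding table by randomized arm is planned. The synopsis gives the endpoint: "The primary safety outcome is a composite of major bleeding events or clinically relevant non-major bleeding events during the Treatment Phase".

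Dose timing differs by arm. Section 5.2.1 places SelK2 "at least 12 hours prior to but not longer than 24 hours prior to the start of the TKA surgery". Section 5.2.2 schedules the first enoxaparin dose 12 hours after surgery, with a further dose 12 hours before surgery at the investigator's discretion. For the combination arm, Section 5.2.3 says: "Additionally, patients will receive 40 mg enoxaparin administered via SC injection 12 hours after TKA surgery".

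Section 3.4.2 starts the Treatment Phase at the first dose, "or the TKA (for enoxaparin arm, if enoxaparin dosing is only done after TKA) up to the day of venography".

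For ongoing life-threatening bleeding, Section 6.5.2.1.1 lists as a recommended step: "Withhold enoxaparin and all other anticoagulant/antiplatelets".

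**The concern.** A dose-based safety set compares arms fairly when dosing comes before the risk period in every arm. Here that holds for SelK2 but not for enoxaparin started after surgery. Entry to the set for those patients can depend on what happens during the operation and the following hours, when surgical bleeding occurs. The plan also conflicts with itself: the primary safety window for such a patient opens at the operation, before the patient can belong to the set in which that outcome is analysed.

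In the combination arm the question is which group the patient is counted in. SelK2 puts the patient in the set, but treatment actually received is not defined for someone who then never gets enoxaparin. The natural reading is SelK2 alone, an arm that Section 5.1.3 describes as closed by then. The trial is open-label (Section 5.1.2) and populations are assigned shortly before data lock (Section 10.2). Without a written rule, the choice could be made knowing both arm and outcome.

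At stake are the bleeding comparison of SelK2 with enoxaparin, where the bias runs against SelK2, and the absolute bleeding rate of the combination, which the adaptive arm is meant to assess (Section 2.0).

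**Working it through.** The plan states no bleeding rate, so there is no figure to reproduce. The check sets dose times against the Safety rule and then illustrates the size.

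**1. Entry to the set against the start of the window**

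| Group | Scheduled dosing | Enters Safety set | Window opens (3.4.2) |
|---|---|---|---|
| SelK2 | 12–24 h before surgery (5.2.1) | Before surgery | At SelK2 dose |
| Enoxaparin, with optional pre-operative dose | From 12 h before surgery (5.2.2) | Before surgery | At that dose |
| Enoxaparin, without it | From 12 h after surgery (5.2.2) | Only once dosed after surgery | At surgery |
| SelK2 + enoxaparin | SelK2 12–24 h before, enoxaparin from 12 h after (5.2.3) | Before surgery, through SelK2 | At SelK2 dose |

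Only the third row has a window that opens before the patient can be in the set. Enoxaparin is taken to be study drug, as in Section 5.1.4.

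**2. SelK2 against enoxaparin**

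Inputs: n = 95 per arm (Section 4.0). Assumed: e = 5 major or clinically relevant non-major bleeds in each arm as randomized, of which k enoxaparin bleeders never receive any dose. The Safety rate for enoxaparin is (e − k)/(n − k).

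| k | Enoxaparin as randomized | Enoxaparin, Safety set | SelK2 | Spurious difference (points) |
|---|---|---|---|---|
| 1 | 5/95 = 5.3% | 4/94 = 4.3% | 5.3% | +1.0 |
| 2 | 5.3% | 3/93 = 3.2% | 5.3% | +2.0 |
| 3 | 5.3% | 2/92 = 2.2% | 5.3% | +3.1 |

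The step of about 1 point per excluded bleeder depends little on e. For k = 1, e = 3 gives 3.16% to 2.13%, and e = 10 gives 10.53% to 9.57%.

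If a share u of these patients had the optional dose, k becomes k(1 − u). For e = 5 and k = 1, u = 0.5 gives 4.5/94.5 = 4.8%, a shift of 0.5 point. With u = 1 the shift is zero.

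**3. How large k might be**

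Write k = 95 × p × f × w, with p the true bleeding rate, f the share of bleeds that start before the first post-operative dose, and w the chance that such a bleeder never receives enoxaparin. None of the three is in the documents. Taking p = 6% (5.7 events) and f = 20–40%:

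- w = 5–20%: k = 0.06 to 0.46, observed rate 5.9% to 5.5%.
- w = 50–100%: k = 0.57 to 2.28, observed rate 5.4% to 3.7%.

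**4. Combination arm, if partly treated patients are counted as SelK2 only**

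With e = 5 and k = 2, the combination falls from 5.3% to 3/93 = 3.2%. SelK2-only rises from 5.3% to 7/97 = 7.2% if it holds 95 patients. If it closed at an assumed 48, its expected events are 48 × 5/95 = 2.53, and the rate becomes 4.53/50 = 9.1%.

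**5. Combination against enoxaparin**

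Both arms can lose events here. Suppose true counts of 8/95 and 5/95, a difference of 8.42 − 5.26 = 3.16 points. If each arm loses two bleeders, 6/93 − 3/93 = 3.23 points, practically unchanged. If the combination loses two and enoxaparin one, 6/93 − 4/94 = 6.45 − 4.26 = 2.20 points, an attenuation.

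**The case against.** A reader might infer that every patient whose post-operative enoxaparin is withheld after a bleed leaves the enoxaparin arm. The documents do not support that. One dose at any time is enough, and dosing runs to Day 11 ± 2, so a skipped or delayed first injection does not remove anyone who is dosed later or who had the pre-operative dose. The explicit withholding step is a recommendation for life-threatening bleeding only, and nothing extends it to the whole composite. Section 8.1 does let the investigator stop study drug for safety, and a peri-operative death also prevents dosing, so never-dosed bleeders are possible, but high values of w have no source.

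A reader might also infer that the plan moves combination patients to SelK2-only. It does not say so; that is the natural reading of an undefined term. Sections 3.4.4 and 6.3.1 still offer a pre-operative enoxaparin dose in the combination arm, and Section 5.2.3 does not.

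Nor do these patients vanish. Section 10.4.1 lists all adverse events, including those before treatment, and provides narratives for deaths and serious events. Section 10.3.2.1 reports randomized and Safety counts. The Steering and Safety Committee reviews accumulating data by group. The loss is from the summary tables.

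Finally, safety analysis is descriptive, with no bleeding hypothesis or margin, and a dosed, as-treated set is a common convention.

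All of this stands and limits the size of the problem. It does not remove the difference between arms in when a patient can enter the set, or supply the missing rule.

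**Conclusion.** The point holds in a limited form. Inclusion in the bleeding tables depends on a post-operative dose for enoxaparin patients without the optional dose, and not for SelK2 patients, while the protocol's own window already runs from surgery. The direction is known: enoxaparin bleeding is understated against SelK2. If partly treated combination patients are counted as SelK2-only, the combination's absolute rate is understated too, while its difference from enoxaparin is roughly preserved or attenuated.

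The size is about 1 percentage point per excluded bleeder in a 95-patient arm. How many there would be is unknown and probably small, since it depends on pre-operative dosing practice and on how many early bleeders never receive enoxaparin, and the documents give neither. With few events expected, one to three such patients could still change how the bleeding comparison reads. This should be fixed, with moderate confidence; it is not a critical flaw.

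**What to change.** - In Sections 10.2 and 10.4, analyse adjudicated major and clinically relevant non-major bleeding, and deaths, in all randomized patients who received any study drug or started the operation, by randomized arm. Reassign only a patient given a wrong product in error.
- State that a combination patient who received SelK2 stays in the combination arm whether or not enoxaparin was started.
- Keep the present tabulation (at least one dose, treatment actually received) as a sensitivity table.
- Reconcile Sections 3.4.4 and 6.3.1 with Section 5.2.3 on pre-operative enoxaparin in the combination arm. Which is intended is for the sponsor to settle.

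The cost is wording, with no new data: adverse events are already collected from randomization and bleeding is already adjudicated. The downside is that a few patients never given enoxaparin are counted under an enoxaparin-containing arm, which the sensitivity table makes visible.
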